3.5 Definitions

3.5.1 Treatment Failure

Treatment failure is defined as the first occurrence after randomization (Stage 2) or as the first occurrence after re-randomization (Stage 3) of any of the following events:

- Corticosteroid injections or treatment with a new or increased lupus medication, except the occasional use of corticosteroids for reasons not associated with SLE flare (see Section 7.1.2.2, *Prednisone (or equivalent)* for additional information); or
- BILAG flare, defined as any item marked new or worse that could support a BILAG A (severe flare) or 2 organs with items marked new or worse that could support a BILAG B (moderate flare), and if the participant's condition is deemed by the investigator to be "moderately worse" or "much worse" compared to the day of randomization, as assessed by the CGI-C; or
- Premature permanent discontinuation of study-assigned treatment for any reason.

For Stage 2, the reference values for the CGI-C should be the investigator's determination of the participant's condition at the Stage 2 Day 0 Randomization Visit. For Stage 3, the reference values for the CGI-C should be the investigator's determination of the participant's condition at the most recent assessment before the Stage 3 Re-randomization Visit.

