13.4.2 Primary Analysis of Primary Endpoint

The primary endpoint is the cumulative incidence of treatment failure at or before the Stage 2 Week 24 visit. Time to treatment failure is defined as the interval from the day of Stage 2 randomization until the day of treatment failure (as defined in Section 3.2, Primary Endpoint). Participants who withdraw from the study early without evidence of treatment failure will be censored at day of the last assessment they were determined to be failure-free. The risk of treatment failure over the period of Stage 2 randomization through 24 weeks of follow-up will be presented graphically using Kaplan-Meier product limit estimates of the survival function in subgroups defined by treatment arm and by immunologically-homogenous subsets. The Kaplan-Meier estimates of event-free survival and confidence intervals using Greenwood's formula for standard error will be reported by subgroup at Stage 2 Week 24. The primary analysis will be a stratified two-sample test of the cumulative incidence of treatment failure at Stage 2 Week 24 using a 2-sided $\alpha=0.05$.

The ultimate goal of Stage 2 is to evaluate the potential effectiveness of MMF within the 7 previously-identified immunologically-homogeneous clusters for lupus. Regardless of the outcome of the stratified test for the pooled analysis, within-cluster landmark two-sample tests will be performed for comparisons of the cumulative incidence of treatment failure at Stage 2 Week 24 for each cluster. Due to the limited samples sizes anticipated in each immunologically-defined subgroup, no correction for multiple comparisons will be made, and p-values of < 0.10 will be considered notable findings but will be interpreted with caution given the high probability of a family-wise error with multiple comparisons under a strong null hypothesis of no treatment benefit.

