13.4.3 Supportive Analyses of the Primary Endpoint

As a supportive analyses, the risk of treatment failure over the entire 48 week period of Stage 2 will be summarized using Kaplan-Meier product limit estimates, and a stratified log-rank test will be conducted with complete follow-up of participants. Additional covariates including participant and disease characteristics at study entry and in Stage 1 treatment withdrawal, and time-dependent covariates during Stage 2 will be explored in a multivariable Cox models

using main effects and interaction terms. Multivariable models will be fully defined in the statistical analysis plan (SAP). Finally, in addition to considering heterogeneity from immunologically defined subsets and other observed factors, a supportive analysis will explore the use of frailty models to consider variability from additional unobserved factors using random effects terms.

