13.7 Sample Size Considerations

The goal of Stage 2 of the study is to evaluate the potential effectiveness of MMF within previously-identified immunologically-homogeneous clusters of lupus patients. To place these cluster comparisons in the context of a successful trial, target enrollment is based on power to show superiority of MMF over placebo in a pooled lupus population.

In previous studies using BOLD designs in lupus populations [22, 93, 94] where long-acting corticosteroids were administered during the treatment withdrawal stage, survival free-from-failure at 6 months in untreated or placebo-treated participants ranged from 5-20% [25]. These studies included participants with a range of disease activity, had differing rules on implementation of background steroids and different definitions for treatment failure. By limiting steroids and carefully adhering to entry criteria to recruit an appropriate population with active lupus disease activity, and by defining treatment failure to include individuals who receive rescue medications post-randomization or who withdraw from treatment prematurely, a placebo survival at 24 weeks of 15% or less should be achievable. In the MMF arm, a minimum clinically meaningful improvement would be 35% survival at 24 weeks.

A study design with 120 participants randomized 1:1 to placebo or MMF will have between 74% to \geq 95% power if placebo survival at Stage 2 Week 24 ranges from 15% to 10% and MMF survival at Stage 2 Week 24 ranges from 35% to 50% (2-sided, $\alpha=0.05$); power is \geq 80% when MMF survival at Stage 2 Week 24 is at least 37%. Power for a two-sample landmark analysis was computed for a Z-Test with unpooled variance using binomial enumeration.

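### The primary Week 24 test uses no baseline disease-activity value, so any precision that an already recorded score carries is lost; the gain on offer is conditional and modest

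*Combined protocol and SAP*

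**What the plan says.** Section 13.4.2 defines the primary comparison: "The primary analysis will be a stratified two-sample test of the cumulative incidence of treatment failure at Stage 2 Week 24", two-sided at 0.05, in the mITT population. It names no covariate and does not list the strata. Section 3.6 stratifies Stage 2 randomization by gene expression signature (Groups 1 to 4, Group 4 being results unavailable) and by no disease-activity factor.

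Table 8.1 schedules PGA, BILAG 2004, H-SLEDAI and the CGI scales at Screening and at the Randomization visit. Section 8.1.3 dispenses study drug only after that visit's activities are complete, so these are pre-treatment values. Day 0 is also the endpoint's own reference: the flare route to failure in Section 3.5.1 requires worsening "compared to the day of randomization, as assessed by the CGI-C".

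Disease characteristics appear only in Section 13.4.3. There, "Additional covariates including participant and disease characteristics at study entry and in Stage 1 treatment withdrawal" are to be explored in supportive multivariable Cox models, with details left to the SAP.

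On power, Section 13.7 assumes that "a placebo survival at 24 weeks of 15% or less should be achievable" and states: "In the MMF arm, a minimum clinically meaningful improvement would be 35% survival at 24 weeks". Power at 15% versus 35% with 120 participants is 74%, the low end of the range given. The section adds that "power is \geq 80% when MMF survival at Stage 2 Week 24 is at least 37" per cent. These figures come from an unstratified, unadjusted Z-test with unpooled variance.

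**The concern.** If residual activity at randomization predicts failure by Week 24, an unadjusted test treats that predictable variation as noise. The documents make some association plausible. Section 1.2.2 links the earliest flares to probably insufficient steroid during withdrawal. Section 4.2.2 requires improvement relative to Screening but sets no absolute ceiling on Day 0 activity, so participants may start Stage 2 at different levels. Section 13.4.3 itself treats disease characteristics as worth exploring.

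The Cox models in Section 13.4.3 do not recover this precision for the primary question. They estimate a hazard ratio, not a Week 24 risk difference, and they are supportive. What is at stake is a few points of power at the smallest effect the plan calls worthwhile, in a trial whose power there is below 80%.

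**Working it through.** **1. Inputs.** From Section 13.7: 60 per arm, failure-free 15% on placebo and 35% on MMF. From Section 13.4.2: two-sided alpha 0.05. The share of within-arm outcome variance explained by the covariate (R²) is not in the documents; it is an assumption, shown over a range.

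**2. The plan's figure.** Exact binomial enumeration of the unpooled Z-test gives 73.8% at 15% versus 35% (stated: 74%) and 80.7% at 15% versus 37% (stated: at least 80%). By the normal approximation:
- Variance = (0.15×0.85 + 0.35×0.65)/60 = 0.355/60 = 0.00592, so SE = 0.0769.
- 0.20/0.0769 = 2.600, and Φ(2.600 − 1.960) = 73.9%.

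The stated power reproduces.

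**3. Effect of one covariate.** Adjustment multiplies the variance by (1 − R²). The enumerated 73.8% corresponds to a standardized effect of 2.597, so power = Φ(2.597/√(1 − R²) − 1.960).

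| Assumed R² | Correlation | Power | Equivalent unadjusted N = 120/(1 − R²) |
|---|---|---|---|
| 0 | 0 | 73.8% | 120 |
| 0.02 | 0.14 | 74.6% | 122 |
| 0.05 | 0.22 | 75.9% | 126 |
| 0.10 | 0.32 | 78.2% | 133 |
| 0.14 | 0.37 | 80.0% | 140 |

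Reaching 80% needs a standardized effect of 1.960 + 0.842 = 2.802, so R² = 1 − (2.597/2.802)² = 0.14.

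**4. Simulation of the gain.** Logistic outcome, one covariate, no strata, standardized risk difference with influence-function standard error, 6,000 trials per setting:

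| Odds ratio per SD of Day 0 score | Unadjusted | Adjusted |
|---|---|---|
| 1.0 | 74.2% | 74.0% |
| 1.5 | 73.6% | 74.1% |
| 2.0 | 73.6% | 76.5% |
| 2.5 | 73.1% | 78.2% |
| 3.0 | 74.4% | 80.9% |

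The Monte Carlo standard error of each figure is about √(0.74×0.26/6000) = 0.6 point. An odds ratio of 2.5 corresponds to R² of 0.10 on placebo and 0.14 on MMF, in line with step 3.

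**5. The error rate depends on the model.**
- *Large logistic model.* Intercept, treatment, three indicators for the four strata, H-SLEDAI and PGA make 7 parameters. With 15% failure-free in both arms there are only 120×0.15 = 18 failure-free participants. One simulation gave null rejection of 6.7–6.9% (unadjusted 5.9–6.0%), with diverging coefficients in about 40% of runs. A second, assuming 5% in Group 4 and a covariate correlation of 0.6, gave 6.6–7.4% at 15% failure-free, 6.5–7.9% at 10% and about 8.1% at 5%.
- *Linear risk-difference model, one Day 0 covariate, HC2 standard errors.* Null rejection was 5.0–5.1% at 15%. At an odds ratio of 2.7 per SD, power was 78.8% against 74.0% unadjusted. With a useless covariate the loss was about 1.5 points.

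Part of that loss is a correction of size. By enumeration, the plan's unpooled Z-test rejects 5.8% of the time under the null at 15%. With no covariate, HC2 replaces the divisor 60 by 59, and Φ(2.597×√(59/60) − 1.960) = Φ(0.615) = 73.1%, which is 0.7 point of the difference.

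**The case against.** The case for leaving the plan alone is substantial. An unadjusted stratified landmark test is a standard, robust choice for a sparse binary outcome in a 120-person Phase 2 trial. The figure of 74% is the least favourable corner of the stated range, and 37% on MMF already gives 80%. It was also computed without strata, so prognostic gene-signature groups may recover some precision in the test actually planned.

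The prognostic strength is unknown and could be weak. Every randomized participant must be moderately or much better on the CGI-C, which may narrow Day 0 scores. H-SLEDAI looks back 28 days (Section 8.2.4.1) and BILAG four weeks (Section 19.3.2), while Stage 1 lasts at most four weeks, so their Day 0 values can still reflect disease before the injection. The flare route counts worsening from Day 0, which partly removes the starting level. Failure also includes discontinuation for any reason, which dilutes the association.

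All of this stands, and it bears on the size of the gain and the choice of covariate. It does not supply a reason to leave a pre-treatment value out of the primary test when a small model holds its error rate.

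A reader might infer more: that Day 0 activity will differ greatly between participants, that adjustment cannot hurt, or that several activity scores can be added to a logistic model at no cost. The documents give no spread of Day 0 scores. Step 5 shows a small loss for a useless covariate and an inflated error rate for the large model.

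**Conclusion.** The point holds as a modest improvement, not as an error in the plan. The primary test uses no baseline disease-activity value although three are recorded at randomization. Under assumed R² of 0.05 to 0.14, adjusting for one of them would raise power at 15% versus 35% from 74% to about 76–80%. If the covariate is not prognostic, the result is roughly no gain or a loss of 1 to 2 points.

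It would be wrong to read this as showing that the trial is underpowered and that adjustment restores 80%. That needs an R² of about 0.14, close to a threefold odds ratio per SD, and nothing in the documents supports or excludes such a value. The calculations also assume complete Week 24 status; Section 13.7 states no allowance for dropout.

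**What to change.** In Section 13.4.2, before unblinding:

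- Make the primary estimate a covariate-adjusted Week 24 difference in failure risk in the mITT population. Include treatment, the stratification groups and one continuous covariate. State which strata are meant, and pool or otherwise handle the small Group 4 to avoid separation.
- Prefer Day 0 PGA as the covariate, because Section 8.2.4.3 has it rate current activity. State how a missing value is handled.
- Use a linear risk-difference model with a small-sample robust (HC2-type) standard error, fitted to pseudo-values where there is censoring.
- Check its type I error by simulation, strata included, over failure-free rates of 5–20%, the range that Section 13.7 reports for earlier untreated or placebo groups.
- Keep the present stratified test as a sensitivity analysis.
- In Section 13.7, describe any gain as conditional on the assumed R².

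No new data are needed. The costs are a slightly more complex primary method, one covariate fixed in advance, a short simulation, and the risk of losing 1 to 2 points of power if the covariate proves uninformative.

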In addition, a simulation study was conducted to determine the power for the supportive analysis using log-rank tests for time until treatment failure under assumptions of non-constant and non-proportional hazards based on the results of previous studies using BOLD designs in lupus populations [22, 93, 94]. Specifically, under an assumption the baseline hazard doubles at Week 12 with an attenuation of long-acting corticosteroids, a proportional hazard corresponding to an increase in survival at Stage 2 Week 24 from 15% to 35% with MMF (HR = 0.55) results in 80.0% power. When all treatment benefit from MMF is restricted to after Week 12, power of the log-rank test decreases to 61.3%, but there remains power to detect larger treatment effects (power = 87.9% when SMMF,24 = 45% and SPlacebo,24 = 15%).

The baseline immunologic cluster would be a useful marker for identifying individuals with a propensity to respond to MMF if some clusters have a very poor response and others have a large response. Hence, the by-cluster comparisons are powered to identify clusters with an MMF response of 60-80% survival at Stage 2 Week 24, which is well above that expected for the overall population.

Table 13.1 gives the number required per arm in a given cluster to achieve 80% power to detect large differences in survival over 24 weeks between arms (based on log-rank test, $\alpha=0.1$, 2-sided). For example, if the underlying placebo survival is 10% at 24 weeks, then 6-9 per arm within a given cluster gives 80% power to detect survival in the MMF arm ranging from 60-80%. Power for within-cluster comparisons will be maximized if numbers per arm are equal. Although stratifying randomization by baseline cluster assignment (7 clusters) is not feasible, stratification by gene expression signature (3 levels) serves as a first-cut approximation to the cluster assignment and should facilitate balance between arms.

Table 13.1. Cluster comparisons: # per arm to achieve 80% power on comparison of survival over 24 weeks

		*Survival at Stage 2 Week 24: MMF				
		60%	65%	70%	75%	80%
*Survival at Stage 2 Week 24: Placebo	5%	7	6	6	5	5
	10%	9	8	7	6	6
	15%	13	11	9	8	7

* Assumed underlying %survival in the population of MMF (or placebo) -treated patients.

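### The aim is to learn in which immunologic clusters MMF works, but the plan has seven separate within-cluster tests at p < 0.10 and no named comparison of the effect across clusters

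*Combined protocol and SAP*

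**What the plan says.** The primary objective (section 2.2) assumes that MMF helps only a portion of patients with lupus. Section 13.4.2 gives the ultimate goal of Stage 2 as to "evaluate the potential effectiveness of MMF within the 7 previously-identified immunologically-homogeneous clusters for lupus". Section 13.7 adds that the baseline cluster "would be a useful marker for identifying individuals with a propensity to respond to MMF" when response is very poor in some clusters and large in others. Section 9.1 plans to ask whether response concentrates in one or two clusters.

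The planned inference is a pooled stratified test at two-sided 0.05. Then, whatever its result, "within-cluster landmark two-sample tests will be performed for comparisons of the cumulative incidence of treatment failure at Stage 2 Week 24 for each cluster". For these, "no correction for multiple comparisons will be made, and p-values of < 0.10 will be considered notable findings". The hypotheses in section 13.6 compare MMF with placebo inside each cluster; none compares the size of the effect between clusters.

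Section 13.4.3 allows exploratory Cox models of additional covariates "using main effects and interaction terms" and mentions heterogeneity from the immunologic subsets when it introduces frailty models. It names no treatment-by-cluster term and leaves the models to a SAP.

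**The concern.** A marker predicts response to a drug only if the drug's effect differs across levels of the marker. Seven separate tests do not address that. A p-value below 0.10 in one cluster and above it in another is compatible with identical effects, above all when each test has 8 or 9 patients per arm.

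The error at stake is a false non-responder cluster: MMF works everywhere, but most clusters miss p < 0.10 and are read as unresponsive. Section 13.4.2 does warn about family-wise error, but under a null of no benefit. That warning concerns false responders and does not cover this case.

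**Working it through.** **Inputs.** 120 participants, 60 per arm; failure-free survival at Week 24 of 15% on placebo and 35% on MMF (section 13.7); 7 clusters and p < 0.10 (section 13.4.2), taken as two-sided as in Table 13.1 ("based on log-rank test, $\alpha=0.1$, 2-sided"). Section 13.4.2 does not name the landmark statistic. The check uses the one that section 13.7 gives for the pooled comparison ("Power for a two-sample landmark analysis was computed for a Z-Test with unpooled variance using binomial enumeration"), and alternatives follow. Assumptions: no censoring (no dropout rate is given) and even clusters, so 60 per arm splits as 9, 9, 9, 9, 8, 8, 8.

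**The plan's own figures.** Z = (p̂_M − p̂_P) / √{[p̂_M(1 − p̂_M) + p̂_P(1 − p̂_P)] / n}. Power is the sum of the binomial probabilities of all outcomes with |Z| above the critical value. With n = 60 and two-sided 0.05:
- 15% vs 35%: 73.8% (stated 74%).
- 15% vs 37%: 80.7% (stated at least 80%).
- Chance that a cluster has 11 to 24 members, Binomial(120, 1/7): 93.3% (stated above 90%).

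**Same benefit in all seven clusters.** The same enumeration at two-sided 0.10 (|Z| > 1.645), 15% vs 35%:
- Power is 0.319 with 9 per arm and 0.282 with 8 per arm.
- Expected notable clusters: 4 × 0.319 + 3 × 0.282 = 2.12.
- P(none notable) = (1 − 0.319)⁴ × (1 − 0.282)³ = 0.080.
- P(all notable) = 0.319⁴ × 0.282³ = 0.0002.
- P(mixed) = 1 − 0.080 − 0.0002 = 0.920.

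On average 7 − 2.12 = 4.88 clusters in which MMF works are not notable.

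**Dependence on the test and on the effect.**

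| Test, uniform 15% vs 35% | P(mixed) |
|---|---|
| Unpooled Z | 92.0% (92.9% with random cluster sizes) |
| Log-rank, hazard doubling at Week 12 | 90–92% |
| Pooled Z | 83% (88% with random sizes) |
| Fisher | 54% (63% with random sizes) |

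Other uniform effects in the plan's range, unpooled Z and even sizes: 10% vs 35%, 97%; 15% vs 50%, 98%; 10% vs 50%, 94%. With no effect in any cluster: 1 − 0.9⁷ = 52% at the nominal level, and 26–46% by enumeration at placebo survival of 10–15%.

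**True heterogeneity, for contrast.** Two clusters (9 per arm) at 70% on MMF and five at 20%, placebo 15%. A 70% cluster is notable in about 83% of trials and a 20% cluster in 10–12%. The mean count is 2 × 0.835 + 2 × 0.122 + 3 × 0.102 = 2.2.

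**One heterogeneity test.** With 0.5 added to the counts, let d_k be the risk difference in cluster k, w_k its inverse variance and d̄ the weighted mean. Then Q = Σ w_k (d_k − d̄)², on 6 degrees of freedom. In 200,000 simulated trials with a uniform 15% vs 35%, the nominal chi-square cut-off at 0.10 rejects in 6.7%; a cut-off of about 9.5 rejects in 10%. Power with that calibrated cut-off, placebo 15%, two high clusters of 9 per arm:
- 80% in two, 15% in five (overall (18 × 0.80 + 42 × 0.15)/60 = 34.5%): about 92%.
- 70% in two, 20% in five (overall 35%): about 70%.
- 60% in two, 25% in five (overall 35.5%): about 42%.

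The same fixed cut-off has a true size of about 7% at a uniform 5% vs 30% and 12% at 15% vs 50%, so the calibration must follow the fitted common effect.

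**The case against.** Five points can be made for the plan.

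- **The research question is partly within-subset.** Section 2.1.1 asks whether there are subsets in which MMF is effective, and a within-cluster test answers that. This stands, and is why those tests should stay. It does not cover the predictive use in section 13.7.
- **The cluster tests are informative under strong heterogeneity.** A reader might infer from the similar mean counts (2.1 and 2.2) that a uniform effect and strong heterogeneity look alike. The plan's figures do not support that. Only the average count is similar; under strong heterogeneity the flags fall mostly on the right clusters (83% against 10–12%). Section 13.7 aims the tests at clusters with 60–80% survival on MMF, where they do discriminate.
- **The 92% is conditional.** A reader might take it to apply whenever effects do not differ. It needs the same non-zero benefit everywhere. With no benefit anywhere the figure is at most about 52% with even clusters, and section 13.4.2 already concedes that risk.
- **Interaction is not ruled out.** Section 13.4.3 leaves room for interaction terms, and section 13.4.2 promises Kaplan–Meier estimates with intervals by arm and subset. So it would be too strong to say that the plan excludes a treatment-by-cluster analysis. But none is named, and intervals for each arm are not intervals for the effect.
- **A heterogeneity test has limited power.** At about 42% for two clusters at 60%, requiring it before any cluster could be called promising would often suppress a real finding in an exploratory Phase 2 analysis. This stands, and argues against using it as a gate.

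**Conclusion.** The concern holds in a bounded form. The plan seeks differences in effect between clusters and specifies only separate cluster tests. If MMF gave 35% against 15% in every cluster, about 2 of 7 clusters would be notable and about 5 would not. Mixed results would occur in about 92% of trials with the unpooled Z, and in 54–92% across the tests considered. The figures assume even clusters and no censoring; random cluster sizes change the unpooled-Z figure little (92.9%). The plan's cautions about cluster p-values do not address false non-responder clusters under a common benefit. The pooled primary analysis is unaffected.

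**What to change.** In section 13.4.2:

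1. Pre-specify one treatment-by-cluster heterogeneity test at Week 24, two-sided 0.10, with its small-sample calibration defined in the SAP, for example a parametric bootstrap under a fitted common effect.
2. Report each cluster's MMF–placebo difference with a confidence interval. Shrunken estimates are optional.
3. State that a notable p-value in one cluster and not in another is not by itself evidence that the effects differ.
4. Keep the within-cluster tests as planned, and do not make them conditional on the heterogeneity test.
5. State the power of the heterogeneity test: about 90% for two clusters at 80% and the rest at 15%, about 70% for two at 70% and the rest at 20%, and about 40% for two at 60% and the rest at 25%. A non-significant result is then not read as proof of a uniform effect.

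The cost is one extra analysis of data already collected and more guarded claims about individual clusters. Sample size and conduct do not change.
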